Roughly 50% of patients enrolled into this quality improvement program will be allocated into an “education first” pathway, which will provide 4 weeks of digital, paper, and customized video resources to explain the medical rationale and anticipatory guidance regarding diabetes care and therapeutics with proven benefit prior to becoming eligible for medical therapy prescription. In addition to looking at uptake and adherence, we will be measuring baseline and end-of-study Patient Activation Measures for each participant. Patient Activation Measures have been shown to correlate with increased self-care behaviors, medication adherence, and diabetes monitoring (11).

Primary Aim

The primary objective of this study is to create a remote diabetes management platform that compared to baseline, will improve initiation and adherence to contemporary guidelines regarding the use of glucose-lowering medications with cardiovascular and renal benefit for patients with type 2 diabetes and high cardiovascular and/or renal risk.

Secondary Aim(s)

- Evaluate optimal timing of patient education within the program. (measured as prescriptions by randomization arm, prescriptions at 2 months, and patients on therapy at end of study)
- Increase patient disease knowledge, activation, and engagement (as measured with short-form Patient Activation Measure)

Exploratory Aim(s)

Weight and HbA1c

We will compare age, socioeconomic demographics (where available), baseline characteristics and medical history, HbA1c, and demonstrate that they are evenly distributed in the population and between groups. We will report subgroup-specific rates if there are significant differences (e.g., evidence of heterogeneity).

Data Sources

Data will be collected from the electronic health record (HER) and directly from patients. All data will be stored in an encrypted, secure database within the Mass General Brigham firewall and using HIPAA-compliant applications.

Study Sample Size

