Primary Outcome: By design, no patients will be on SGLT2i or GLP-1 RA therapy at baseline. We are excluding patients who are on the drugs of interest at baseline, so our primary outcome is the proportion of prescription therapy provided at 6 months. Our null hypothesis is that with we would expect with our education only (control) arm to increase rate of prescription from 0% to 5% based on secular trends and from 0% to 20% increase in SGLT2i or GLP-1 RA therapy in our intervention group utilizing navigators. 100 patients per arm will allow a 25% dropout rate to maintain power > 80% to maintain an alpha level of 0.05. As we are comparing the timing of education in the A/B allocated groups, we expect that our sample size will provide ~80% power to detect an absolute rate of prescription difference of 15% between our immediate titration and education prior to titration groups (i.e., at 3 months)

Secondary Outcomes: With a mean HbA1c of 7.2% and a standard deviation of 1%, to obtain 80% power to detect a 0.5% difference in HbA1c, we would need to enroll 63 patients per arm (preliminary data.) To account for dropout, (expecting 25% dropout) we will calculate $N1 = n/(1 - \text{dropout rate}) \Rightarrow 63/0.75 = 84$ patients per arm.

Data Management

Mass General Brigham will create a data collection instance within the patient-management application. All data will be collected and stored within the Mass General Brigham firewall in a HIPAA-compliant, encrypted server, key variables data will be randomly sampled and verified for accuracy in 40 patients representing 20% of the study population. Data will be stored for at least 5 years after project completion.

Data Analysis

We will utilize SAS software, version 9.4 (SAS Institute) to conduct our statistical analysis.

There will be ongoing quality checks of the data. Before final analysis, the data will be queried for outliers and missing data. The primary analysis will not impute any missing data though sensitivity analysis may use imputation methods such as last observation carried forward (LOCF).

Definition of Analysis Sets

For the Full Analysis Set (FAS) Patients will be included all patients enrolled (intention-to-treat analysis.)

The Per protocol Set (PPS) will include patients that did not drop out or become unreachable and completed the entire quality improvement program.

Statistical Methods

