For our primary outcome, the percent of patients on either an SGLT2i or GLP-1 RA from baseline to conclusion of the study at 6 months post-enrolment, we will perform a Chi-Square test to determine a difference in the terminal rates at the end of the study to determine treatment effects between groups.

We will develop a cumulative incidence curve displaying patients both prescribed and taking DRIVE medications for the duration of the program.

We will perform t-tests and Fisher's exact test for the baseline univariate analysis. As we will be utilizing A/B allocation there should be no bias or confounding at baseline, however if any significant differences are found, we will correct for these utilizing logistic regression. A/B allocation with 200 patients should cause any confounders to balance between the groups. We will also perform a longitudinal model for binary outcome at 6 months. For our co-secondary outcomes, the change in the HbA1c, and PAM from baseline to the end of the 6-month study, these will be analysed with a paired t-test and we will report a mean and standard deviation. A secondary analysis will be to conduct linear regression models with two variables (baseline HbA1c and baseline weight) to control for any confounders.

We will conduct our analysis via the intention-to-treat principle with two-sided type I error with an alpha of 0.05. For participants with missing outcome data, we will perform a sensitivity analysis with missing outcomes excluded or included as an event.

A priori sub-analyses will be performed based on zip code, baseline HbA1c, race, insurance status, and sex with a p-value threshold of 0.1 for these secondary analyses and we will account for multiple testing. A cox proportional hazards model will be performed to assess time-to-prescription between groups.

After the final data was reviewed, a series of subsequent hypotheses were identified for additional analysis. These analyses are, by definition, post hoc and, therefore, considered hypothesis-generating. A p-value of 0.05 will be considered significant without any correction for multiple comparisons.

Interim Analysis

N/A

Quality Control

Data will be collected from our EHR, the MGB Electronic Data Warehouse (EDW), and patients. Clinical laboratories within MGB system have laboratory certificates available upon request.

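### The SAP makes reporting of subgroup rates depend on significance and does not say whether this governs the five a priori sub-analyses; all five should be reported whatever the p-value

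*SAP*

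**What the plan says.** Two places in the SAP bear on subgroup results.

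- **Exploratory Aim(s).** A sentence on baseline comparability covers age, socioeconomic demographics, baseline characteristics, medical history and HbA1c. Its purpose is to "demonstrate that they are evenly distributed in the population and between groups". The next sentence is the reporting rule: "We will report subgroup-specific rates if there are significant differences (e.g., evidence of heterogeneity". It gives no test, threshold or list of subgroups.
- **Statistical Methods.** "A priori sub-analyses will be performed based on zip code, baseline HbA1c, race, insurance status, and sex", and the sentence continues "with a p-value threshold of 0.1 for these secondary analyses and we will account for multiple testing". It does not name the interaction test, the levels or cut-points of the factors, or the multiplicity method. It neither makes reporting conditional nor promises that every result will be shown.

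No other section of the protocol or SAP commits to showing estimates and intervals for all five factors.

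**The concern.** A rule that shows subgroup rates only after a significant result filters estimates on their size. In a small trial, the estimates that pass are on average larger in absolute size than the true difference, and those that fail are not seen. If the rule reaches the five planned factors, a reader who finds no rates by race, sex, insurance or zip code cannot tell a close null from an imprecise estimate. Where rates do appear, the contrast will tend to be too large. These factors bear on who benefits from a program meant to raise uptake of guideline therapy, so the direction and precision of every result are useful, including the null ones.

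**Working it through.** **1. Inputs from the SAP.** Study Sample Size assumes 5% v 20% ("increase rate of prescription from 0% to 5% based on secular trends and from 0% to 20% increase") and states: "100 patients per arm will allow a 25% dropout rate to maintain power > 80% to maintain an alpha level of 0.05". Statistical Methods sets a two-sided alpha of 0.05 overall and a threshold of 0.1 for the five sub-analyses.

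**2. The plan's own figure.** Two proportions, two-sided 0.05, 80% power, pooled rate 0.125:

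n = [1.96·√(2·0.125·0.875) + 0.8416·√(0.05·0.95 + 0.20·0.80)]² / 0.15² = (0.917 + 0.383)² / 0.0225 ≈ 75.1, so 76 per arm. Then 76/0.75 = 101.3, so 102. The stated 100 per arm is close. At 75 evaluable per arm, power is 79.9% by the normal approximation and 82.7% for the exact chi-square test. The SAP gives no power figure for subgroups.

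**3. Assumptions not in the documents.** Each factor has two levels split 50/50. Each arm-by-level cell then holds 50 patients, or about 37 after 25% dropout. The test is a Wald test on the difference between the two subgroup risk differences.

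**4. Precision of that difference.** SE = √[2·(0.05·0.95)/n + 2·(0.20·0.80)/n] = √(0.415/n).

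- n = 50: SE = 9.1 points. Smallest difference that passes p < 0.1: 1.645 × 9.1 = 15.0 points.
- n = 37.5: SE = 10.5 points. Smallest difference that passes: 1.645 × 10.5 = 17.3 points.

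Any true difference below 15 points can therefore be shown only if it is overestimated.

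**5. Simulation.** 200,000 trials per row, with 5% in the comparator in both levels. Intervention effects are 15 and 15, 20 and 10, or 25 and 5 points, so the true difference is 0, 10 or 20.

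| True difference | Per cell | Flagged, p < 0.1 | Mean absolute difference shown | Flagged, p < 0.02 | Mean absolute difference shown |
|---|---|---|---|---|---|
| 0 | 50 | 11% | 18 | 2.3% | 24 |
| 0 | 37 | 11% | 21 | 2.3% | 27 |
| 10 | 50 | 31% | 20 | 12% | 25 |
| 10 | 37 | 26% | 23 | 9% | 28 |
| 20 | 50 | 74% | 24 | 49% | 27 |
| 20 | 37 | 63% | 26 | 36% | 30 |

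The normal approximation gives similar results. With a true 10 points it flags 30% (shown as 20.7 points) at 50 per cell and 25% (shown as 23.5 points) at 37.5. Without the filter, the estimate averages 10 points when the truth is 10, and 20 when it is 20.

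**6. Multiplicity.** For five independent tests with no true heterogeneity, the chance of at least one flag is 1 − 0.9⁵ = 41% at 0.1 each. With Bonferroni (0.1/5 = 0.02 each) it is 1 − 0.98⁵ = 9.6%. Bonferroni is an assumption. The last two columns show that the stricter threshold flags less often but enlarges what is shown.

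**The case against.** The best defence is that the reporting rule has nothing to do with the five factors. It follows a sentence on baseline balance whose variables are not the list in Statistical Methods, so the significant differences could be baseline differences. It may also state an ordinary convention: give stratum-specific rates where there is heterogeneity and the pooled rate otherwise. The five factors are prespecified, multiple testing will be accounted for, and the results are secondary.

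Much of this stands, and it rules out several stronger readings that a reader might infer:

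- **That the plan commits to withholding null results for the five factors.** No sentence says so. The link between the two places is an inference, because the SAP leaves it unstated.
- **That 41% is the plan's false-flag rate.** The sentence that sets the 0.1 threshold also promises to account for multiple testing. The 41% describes only the unadjusted case.
- **That any flagged difference is mostly noise.** This depends on the true heterogeneity. For a true 20-point difference the exaggeration is about 1.2- to 1.3-fold.
- **That readers would not know how many factors were planned.** Statistical Methods names all five.

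The defence does not remove the problem. Subgroup-specific rates and heterogeneity read more naturally as outcome results than as baseline balance, and Statistical Methods has its own remedy for baseline imbalance (logistic regression). Even on the baseline reading, whether subgroup rates appear would depend on a significance test. Multiplicity control limits false flags but does not make the reporting complete.

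**Conclusion.** The concern holds as a conditional one. The SAP states a significance-dependent reporting rule for subgroup rates, does not say how it applies to the five a priori sub-analyses, and nowhere promises full reporting. If the rule is applied to them at p < 0.1, a true 10-point difference in effect is shown at about twice its size or a little more, and about seven times in ten or more it is not shown at all. A true 20-point difference is only mildly inflated. These sizes rest on a 50/50 two-level split, 5% v 20% on average and a Wald interaction test. Zip code, race and insurance status may have more levels or unequal ones; a 30/70 split gave similar or larger exaggeration. The primary analysis, its alpha and the sample size are unaffected.

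**What to change.** Replace the conditional sentence under Exploratory Aim(s) with:

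> For each of the five a priori factors, arm-specific rates, the risk difference with 95% CI and the arm-by-subgroup interaction test will be reported for all levels, whatever the p-value.

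Apply the multiplicity adjustment promised in Statistical Methods to the five interaction tests, naming the method, and state the levels or cut-points of each factor. If the original sentence was meant only for baseline comparisons, say so there.

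The cost is one extra table or forest plot with wide intervals. No new data are needed, and neither the sample size nor the primary analysis changes.

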¹ ASCVD for this project is defined as history of myocardial infarction, angina, unstable angina, coronary revascularization, percutaneous coronary intervention, transient ischemic attack (TIA) stroke, peripheral artery disease, carotid artery disease ($> 50\%$ luminal obstruction)

² Hypoglycemia for this project is defined as a blood sugar $< 70 \text{ mg/dL}$

Patients recruited into the program will enter either 1) a gradual education period for 2 months followed by pharmacist and navigator-based medication titration, or 2) rapid education in conjunction with pharmacist and navigator-based medication titration via a Collaborative Drug Therapy Management (CDTM) algorithm designed to improve medical therapy for the treatment of type 2 diabetes with cardiorenal comorbidities. The CDTM will be approved by the BWH Pharmacy and Therapeutics committee. We will use A/B testing to optimize the timing of the educational program. Outcomes will include percentage of patients prescribed SGLT2i or GLP1-RA, percentage of prescriptions filled, HbA1c, change in the diabetes treatment satisfaction questionnaire short (DTSQs) score, and Patient Activation Measure (PAM) at enrollment and completion of the program.

Participants whose HbA1c rises to 9.0-9.9% following enrollment as part of their program baseline labs will automatically be assigned to immediate pharmacist and navigator-based medical titration and rapid education. As a result, participants with baseline HbA1c between 9.0-9.9% will remain in the program but will not be part of the A/B testing.

We will generate prototype software to guide DM medication changes based on patient-specific information and to longitudinally monitor each participant's progress through the algorithm and document

clinical and laboratory information. Basic patient demographic, laboratory, medication, and medical history data will be housed in a secure platform database for clinical management and communication.

Briefly describe study procedures. Include any local site restrictions, for example, “Subjects enrolled at Partners will not participate in the pharmacokinetic portion of the study.” Describe study endpoints.

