Potential participants will be screened for eligibility through CardioCompass – an application housing medical data currently in use at DCT – as well as the EHR as described in protocol 2020E000255. If eligible, the patients will be contacted by navigators trained to describe the study procedures, who will ask them whether they would be willing to participate.

Participants who agree to participate will enter either early pharmacist and navigator-led medical titration and concurrent education, or a gradual titration, through which patients will undergo 2 months of diabetes self-management education followed by pharmacist and navigator-led program of medication optimization. Navigators will contact the patient at regular intervals and monitor symptoms and laboratory tests will be obtained per protocol to ensure safety of the prescribed medications. Any symptoms will be evaluated by the program nurse practitioner or physician and managed per standard of care.

The education program for all patients will follow standard diabetes self-management education curricula, focusing on medication adherence, the role and benefit of medical therapy for the treatment of type 2 diabetes, and other self-management behaviors. We will offer written materials of current guideline recommendations and an online web portal with short educational videos about diabetes, cardiovascular risk, and lifestyle and medical interventions. Educational videos produced by study staff will be made available to participants through the Mytonomy (www.mytonomy.com) web-based portal. In addition, materials from <https://knowdiabetesbyheart.org/> – a collaboration between the American Heart Association and the American Diabetes Association – will be shared with patients virtually. We will also offer live webinar, question/answer sessions for patients and providers to gain education and ask questions regarding the medications and program.

Once each participant has been followed for six months, the intervention will conclude with formal written handoff to the patient’s primary care provider (PCP), and the ongoing monitoring of labs, disease management, health care utilization, health outcomes, and medications will continue beyond the program period as per the patient’s PCP.

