Explain in detail how, when, where, and by whom consent is obtained, and the timing of consent (i.e., how long subjects will be given to consider participation). For most studies involving more than minimal risk and all studies involving investigational drugs/devices, a licensed physician investigator must obtain informed consent. When subjects are to be enrolled from among the investigators' own patients, describe how the potential for coercion will be avoided.

Potential participants will be notified by letter or Patient Gateway message that they will soon receive a call from a navigator about possible enrollment into the program.

The navigator will review the program details with the participant over the phone. The participant can agree to participate during this initial phone call but will also be given the opportunity to ask questions, review written materials, and/or separately speak to their PCP prior to enrollment. There is no time

constraint within which the patient must agree to participate. However, enrollment will be capped at the first 200 patients who agree to participate. The patient's decision to participate or not to participate in this program will be documented in the EHR. The patient will be informed that the decision to participate or not will not affect the care they receive from other providers.

As this project is using FDA-approved medications prescribed according to guideline recommendations and therefore the primary risk to subjects is no more than minimal and no different from standard of care, the study will be conducted with a waiver of consent/authorization.

NOTE: When subjects are unable to give consent due to age (minors) or impaired decision-making capacity, complete the forms for Research Involving Children as Subjects of Research and/or Research Involving Individuals with Impaired Decision-making Capacity, available on the New Submissions page on the PHRC website:

<https://partnershealthcare.sharepoint.com/sites/phrmApply/aieipa/irb>

For guidance, refer to the following Partners policy:

Informed Consent of Research Subjects:

<https://www.partners.org/Assets/Documents/Medical-Research/Clinical-Research/Informed-Consent-of-Research-Subjects.pdf>

DATA AND SAFETY MONITORING

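### The >80% power for the 6-month primary outcome rests on an education-only control arm that the trial does not have, and the planned between-group test addresses education timing, not the primary aim

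*SAP*

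**What the plan says.** **Power basis.** Under Study Sample Size, the SAP makes prescription at 6 months the primary outcome and states "we would expect with our education only (control) arm to increase rate of prescription from 0% to 5% based on secular trends", against 20% in the navigator group. It claims more than 80% power at alpha 0.05 with 100 per arm, allowing for 25% dropout. The next sentence turns to the groups actually allocated (immediate titration, and education before titration). It gives about 80% power for a 15-point difference, at 3 months.

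**Groups.** The protocol (Research Design and Methods) gives one group "a gradual education period for 2 months followed by pharmacist and navigator-based medication titration" and the other titration with rapid education from the start. Its description of procedures repeats that in the gradual group "patients will undergo 2 months of diabetes self-management education followed by pharmacist and navigator-led program of medication optimization". The SAP (Research Question and Objectives) describes an education-first pathway "which will provide 4 weeks of digital, paper, and customized video resources" and places this "prior to becoming eligible for medical therapy prescription".

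**Aims and test.** The SAP's primary aim is a platform that, "compared to baseline, will improve initiation and adherence to contemporary guidelines". Education timing is a secondary aim, measured partly by prescriptions in each arm and by patients on therapy at the end of the study. Statistical Methods assigns the primary outcome a chi-square test of end-of-study rates between groups.

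**Numbers.** The protocol says that "participants with baseline HbA1c between 9.0-9.9% will remain in the program but will not be part of the A/B testing", and in Consent Procedures that "enrollment will be capped at the first 200 patients who agree to participate".

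**The concern.** There are two faults. First, a 5% rate from secular trend alone describes patients whom the program does not treat. By 6 months, patients in both groups have been open to pharmacist- and navigator-led prescribing for most of follow-up, so the stated power belongs to a contrast that the trial does not make.

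Second, the between-group test cannot answer the primary aim. Both groups receive the platform, so their difference shows the effect of when education is given. Baseline use is 0% because current users are excluded, and no whole-cohort estimate is clearly specified to describe the change from it.

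The risk lies in interpretation. A non-significant 6-month chi-square could be reported as a negative result with more than 80% power about the platform, although the test concerns timing and its power has not been established. The data, the estimates and the type I error of the test are unaffected.

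**Working it through.** **Inputs.** From the SAP: two-sided alpha 0.05, 100 per arm, 25% dropout, 5% and 20% at 6 months, and a 15-point difference at 3 months. Evaluable patients per arm: 100 × 0.75 = 75.

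**Formula.** With d = |p1 − p2|, p̄ = (p1 + p2)/2, S0 = √(2p̄(1−p̄)/n) and S1 = √((p1(1−p1) + p2(1−p2))/n), power = Φ((d − 1.96·S0)/S1) + Φ((−d − 1.96·S0)/S1). The second term is negligible except when d is small.

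**Step 1: the SAP's own figure (5% v 20%, n = 75).** p̄ = 0.125; S0 = √(2 × 0.125 × 0.875/75) = 0.0540; S1 = √((0.0475 + 0.16)/75) = 0.0526; (0.15 − 1.96 × 0.0540)/0.0526 = 0.84; power 79.9%. Exact enumeration of the uncorrected chi-square gives 82.7%. With n = 100 the results are 90.0% and 92.1% exact. The calculation is sound for the contrast it describes.

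**Step 2: whether that contrast exists at 6 months.** With the protocol's 2 months of education, 4 of the 6 months remain for titration. With the SAP's 4 weeks, about 5 remain. Neither document holds any group at education only to 6 months, and neither gives an expected 6-month rate for the education-first group.

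**Step 3: power of the comparison that will be made.** The immediate group is kept at the SAP's 20%. The education-first rates below are assumptions, set on both sides because education might raise uptake as well as delay it.

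| Education-first rate at 6 months | Power, 75 per arm | Power, 100 per arm |
|---|---|---|
| 5% (SAP's control figure) | 80% | 90% |
| 10% | 40% | 51% |
| 15% | 13% | 15% |
| 25% | 11% | 13% |
| 30% | 29% | 37% |
| 35% | 54% | 66% |

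Solving for 80% power against 20%, the education-first rate must be at or below about 5.0%, or at or above about 40.9%, with 75 per arm. With 100 per arm the limits are about 6.6% and 37.9%.

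**Step 4: the 3-month statement.** 20% − 5% = 15 points, so a 5% base seems to be implied, and it gives 80% / 90% at 75 / 100 per arm. The same 15 points gives 68% / 80% from a 10% base and 54% / 66% from a 20% base. The statement concerns 3 months and cannot be carried over to 6.

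**Step 5: number per arm.** With enrolment capped at 200 and about half allocated to each pathway, 200/2 = 100 per arm is reached only if nobody leaves the A/B test because of a baseline HbA1c of 9.0-9.9%. So 100 is a maximum. The documents do not say how many will leave.

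**The case against.** The strongest defence is that the two power sentences form one calculation. The 15 points is 20% minus 5%, 5% v 20% at 75 per arm gives almost exactly 80%, and the second sentence names the true groups at 3 months. A low rate in the education-first group is plausible during or soon after the education period. This reading is fair, and it means that the 3-month statement should not be faulted for having no base rate at all. It does not rescue the first sentence, which ties 5% to the 6-month outcome.

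It can also be said that the 6-month proportion is already planned. That is largely right. The SAP names it as the primary outcome, and its remark about hypotheses identified after the final data were reviewed refers to additional analyses. A reader might infer from that remark that the primary outcome was chosen late, but the documents do not show this. What is lacking is a clear whole-cohort presentation with an interval.

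Missing outcomes are partly covered as well: no imputation in the primary analysis, and sensitivity analyses with missing outcomes excluded or counted as events.

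Finally, few patients may leave the A/B set. Screening already requires HbA1c of 6.5-8.9%. The SAP's mean of 7.2% and SD of 1%, taken as normal (an assumption), put about 3% to 4% of patients at 9.0-9.9%, or roughly 6 to 8 of 200. That calls for a note on the maximum, not a claim of serious loss.

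**Conclusion.** The point stands, within limits. The >80% figure is arithmetically correct for 5% v 20% but does not describe the 6-month A/B comparison. The power of that comparison is unknown. With the immediate group at 20%, it falls below 80% for any education-first rate between about 5.0% and 40.9% at 75 per arm (6.6% and 37.9% at 100). These figures rest on the SAP's 20% and on assumed rates for the other group.

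A reader might infer that the trial is underpowered. The documents do not support that, because they give no education-first rate and a large difference in either direction would be detected. Nor is there an arithmetic error or an inflated type I error.

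The mismatch between aim and test is the weightier half. The chi-square answers a secondary question, and the primary aim has no clearly specified whole-cohort estimate. This should be fixed, because it governs how a null result is read.

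**What to change.** 1. **Power text.** Remove the education-only control as the basis, withdraw the >80% claim for the 6-month comparison, and state that both groups are titrated. Give power over a short range of named rates in both directions, at 75 and 100 per arm. Note that 100 is a maximum, given the enrolment cap and the removal of baseline HbA1c 9.0-9.9% from the A/B test.
2. **Chi-square.** Keep it, described as the education-timing comparison in the A/B set. Report the risk difference with a 95% CI, and state that a null result is not evidence against the platform.
3. **Primary aim.** Report the pooled 6-month proportion with an exact 95% CI as an uncontrolled descriptive estimate. Show both prescription provided (Study Sample Size) and patients on therapy (Statistical Methods), so that neither is chosen after the results are seen. Date the added interval and pooled presentation as a correction, without calling the outcome itself post hoc. Show 5% only as an assumed benchmark. Add missing counted as not on therapy to the existing sensitivity options.
4. **Education period.** Reconcile the protocol's 2 months with the SAP's 4 weeks, since the length affects the expected gap between groups.

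**Cost.** Text and reporting only, with no new patients or data. The downside is that a single favourable power figure becomes a less favourable range, and the primary aim rests on an openly uncontrolled estimate.
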